8.8.6 Nasal Lining Fluid

The nasal lining fluid procedure is a quick and simple technique for sampling nasal secretions. Nasal lining fluid samples will be obtained in accordance with the schedule provided in Table 2 in a subset of subjects only participating in the sub-study, and if nasal lining fluid sampling supplies are available. If sputum and nasal collections occur at the same visit, nasal sampling should occur before spontaneous/sputum induction. Nasal lining fluid biomarkers will be measured to evaluate the pharmacology of tezepelumab and to evaluate changes in biomarkers related to COPD, inflammation and the TSLP pathway. Baseline and early post-dose levels of nasal lining fluid biomarkers may also be used to explore for potential predictive biomarkers of response or exposure to tezepelumab. The specific biomarkers that may be analyzed include but are not limited to cytokines, chemokines and inflammatory mediators associated with COPD and the TSLP pathway. Drug concentrations may also be measured in the nasal lining fluid samples, if feasible. If appropriate, urea concentrations may be measured to correct for the dilution factor of the nasal lining fluid samples. The results of these exploratory analyses will not be reported in the CSR but in an addendum, or separately in a scientific report or publication. Detailed procedures for obtaining, processing, storing, transporting and analysing the samples will be described in applicable manual. During the COVID-19 pandemic, nasal samples will only be collected if allowed per local Health and Safety regulations or guidance if sub-study laboratory test kits are available.

The nasal lining fluid samples will be retained at AstraZeneca or designee for a maximum of

15 years following the Last Patient's Last Visit. The results of this biomarker research will not be reported in the CSR but in an addendum, or separately in a scientific report or publication.

8.8.7 Urine Biomarkers

Urine will be collected in accordance to the schedule provided in Table 2. Urine analysis may include but is not limited to biomarkers of inflammation associated with COPD and TSLP pathway. The results of these exploratory analyses will not be reported in the CSR but in an addendum, or separately in a scientific report or publication. The urine samples will be retained by AstraZeneca or a designee for a maximum of 15 years following Last Patient Last Visit.

8.9 Healthcare Resource Utilization and Health Economics

Healthcare resource utilization and health economics data, associated with medical encounters, will be collected in the CRF by the Investigator and study-site personnel for all subjects throughout the study. At randomization, Healthcare Resource Utilization (HRU) information will be collected with a 'one year' recall period. All the subsequent visits will collect HRU information with a recall period of 'since the last scheduled visit'. The data may be used as input to health economic analysis for example cost utility analysis or cost effectiveness analysis. Protocol-mandated procedures, tests, and encounters are excluded. Any results from such analyses may be reported separately from the CSR.

9. STATISTICAL CONSIDERATIONS

9.1 Statistical Hypothesis

The null hypothesis is that the exacerbation rate on tezepelumab is greater than or equal to the exacerbation rate on placebo. The alternative hypothesis is that the exacerbation rate on tezepelumab is less than the exacerbation rate on placebo, i.e.,

 H_0 : Rate ratio (tezepelumab vs Placebo) ≥ 1 H_a : Rate ratio (tezepelumab vs Placebo) ≤ 1 .

9.2 Sample Size Determination

Original Sample Size

For the primary endpoint of reduction in COPD exacerbation rate, 141 subjects per treatment arm (282 total) will be randomized to achieve 80% power of detecting a 30% reduction in tezepelumab versus placebo over a fixed time period of 52 weeks. This calculation has assumed a one-sided 5% alpha level test, an annual placebo rate of 1.6 events/subject/52

weeks, a negative binomial shape parameter of 0.6, and 10% uniform drop out.

In the absence of the interim analysis for futility, this design would provide 81.2% power, and only 136 subjects per treatment arm would be required for 80% power.

This power statement accounts for the power loss associated with the futility interim analysis that was originally planned to occur when 182 subjects had been randomized. In simulated results, 1.2% of simulated trials were stopped early for futility but would have been successful at the final analysis of the primary endpoint had they been allowed to continue. Therefore, the overall power for this trial accounting for the interim analysis is 80%. Note that as a result of the pause in recruitment due to COVID-19, the futility analysis is now planned to occur when approximately 30% of follow-up data are available but the expected power loss will be comparable under these conditions.

The primary endpoint will also be tested using a one-sided 2.5% alpha level test, but the sample size has not been determined based on providing power for this test.

Updated Sample Size

The sample size has been reassessed due to the potential for reduced exacerbation rates due to limited person-to-person contact and exposure to respiratory infections during the COVID-19 pandemic. Assuming the same treatment effect (0.7) and dispersion parameter (0.6) as originally assumed, a sample size of 169 subjects per treatment arm (338 overall) will maintain the study power if the placebo exacerbation rate is as low as 1.2 exacerbations/subject-year.

9.2.1 Estimands

The **Primary estimand** is described as follows:

- Population subjects with moderate to very severe COPD who are randomised and receive at least one dose of IP
- Variable annual rate of moderate or severe COPD exacerbations up to Week 52
- Population-level summary measure exacerbation rate ratio of tezepelumab versus placebo
- Handling of intercurrent events:
 - o Treatment discontinuation: All available data are used regardless of whether treatment discontinuation occurs.

• Use of an alternative biologic: All available data are used regardless of whether subject switches to an alternative biologic therapy.

The **Supplemental estimand** is described as follows:

- Population subjects with moderate to very severe COPD who are randomised and receive at least one dose of IP
- Variable annual rate of moderate or severe COPD exacerbations up to Week 52
- Population-level summary measure exacerbation rate ratio of tezepelumab versus placebo
- Handling of intercurrent events:
 - o Treatment discontinuation: All available data are used up until randomised treatment is discontinued.
 - Use of an alternative biologic: All available data are used up until subject switches to an alternative biologic therapy.

A different approach may be considered depending on the number and pattern of drop-outs. Further detail will be provided in the SAP.

Secondary estimands and estimands to explore the impact of the COVID-19 pandemic may be detailed in the SAP.

9.3 Populations for Analyses

For purposes of analysis, the following populations are defined:

Population	Analysis Set Description
All subjects analysis set	This analysis set comprises all enrolled subjects who signed the informed consent form, including screening failures, and will be used for the reporting of disposition.
Randomized subjects analysis set	This analysis set comprises all subjects randomized to study treatment, irrespective of whether IP was subsequently taken, and will also be used for the reporting of disposition.
Full analysis set (FAS)	This analysis set comprises all subjects randomized to study treatment who received at least one dose of IP, irrespective of their protocol adherence and continued participation in the study.

	Efficacy analyses will be performed using all subjects in the FAS.
	Subjects will be analyzed according to their randomized treatment
	(including in the case of any discrepancies between randomized
	and actual treatment at one or more visits).
PK analysis set	All subjects who received at least one dose of tezepelumab and
	have at least one detectable serum concentration post first dose that
	is not affected by factors such as protocol deviations (e.g.,
	disallowed medication or incorrect study medication received).
Safety analysis	This analysis set comprises all subjects who received at least one
set	dose of IP.
	Safety analyses will be performed using all subjects in the safety
	analysis set. Subjects will be analyzed according to their actual
	treatment in the case of any discrepancies between randomized and
	actual treatment. Specifically, a subject randomized to placebo
	who has on one or more occasion actually received active
	(tezepelumab) treatment will be assigned to the tezepelumab
	group. A subject who has on no occasion actually received any
	active (tezepelumab) treatment will be assigned to the placebo
	group.

9.4 Outcome Measures for Analyses

9.4.1 Definition of Baseline and Subject Baseline Analyses

In general, the last measurement on or prior to the date of randomization will serve as the baseline measurement. If there is no value on or prior to the date of randomization, then the baseline value will not be imputed and will be set to missing. The baseline for outcome variables based on efficacy biomarkers is defined as the value recorded at randomization; if a measurement is not scheduled to be measured at randomization visit or if the randomization visit measurement is missing, the last non-missing value before randomization will be used as baseline instead.

For spirometry, laboratory data and physical examination, baseline will be defined as the latest non-missing assessment prior to first dose.

Absolute change from baseline is computed as

(post-randomization value –baseline value).

Percent change from baseline is computed as

100 x ((post-randomization value – baseline value) / baseline value) %.

If either the post-randomization value or the baseline value is missing, then the absolute or percent change from baseline value will also be set to missing.

9.4.2 Calculation or Derivation of Efficacy Variables

9.4.2.1 Exacerbation Rate

The annual COPD exacerbation rate will be used as the primary efficacy variable.

A COPD exacerbation is defined in Section 8.1.1.

In order to calculate the number of exacerbations experienced by a subject during the treatment period, the following rule will be applied:

The start of an exacerbation is defined as the start date of systemic corticosteroids or antibiotic treatment or hospital admission, whichever occurs earlier, and the end date is defined as the last day of systemic corticosteroids or antibiotic treatment or hospital discharge, whichever occurs later.

Additional systemic corticosteroid treatments, emergency room visits requiring use of systemic corticosteroids, or inpatient hospitalization due to COPD occurring during an exacerbation should not be regarded as a new exacerbation. In order to be counted as a new exacerbation it must be preceded by at least 7 days in which neither criterion is fulfilled.

The follow-up time for exacerbations for a subject is approximately 52 weeks; defined as the time from randomization to the date of Visit 16, regardless of whether subjects remain on randomized treatment. For a subject lost to follow-up or prematurely withdrawing from the study prior to Visit 16, this will be defined as the time from randomization to the time point after which an exacerbation could not be assessed.

The number of days that the subject experiences an exacerbation during the follow-up time, including the subsequent 7 days (when a further exacerbation would not be considered a separate event (and if within the follow-up time) will be subtracted from the follow-up time to give the time at risk of exacerbation.

In the statistical analysis, the number of COPD exacerbations experienced by a subject during their follow-up time will be used as response variable, and the logarithm of the subject's corresponding time at risk will be used as an offset in the analysis to adjust for subjects having different observation times during which the events occur.

For the production of summary statistics, the annual exacerbation rate per subject is calculated, and standardized per 52-week period according to the formula described below.

*Annual exacerbation rate=Number of exacerbations*365.25 / (Time at Risk of Exacerbation).*

For subjects who prematurely discontinue treatment, efforts will be made to continue collecting the exacerbation data until the scheduled Visit 16/EOT at Week 52 after randomization. In the statistical analysis of exacerbation rate for the primary estimand, the data collected up to Visit 16/EOT will be included for the patients who prematurely discontinue treatment according to the intent-to-treat principle. For the patients who died during the treatment period the exacerbation data collected up to the date of death will be included in the statistical analysis.

If the cause of any death is related to COPD or a COPD exacerbation, the event will also be included in the rate calculation as a severe exacerbation.

To examine the sensitivity of results of the primary analysis to the underlying assumptions, sensitivity analyses may be performed using different assumptions for missing data following study withdrawal. Further details will be given in the SAP.

The annual rate of moderate or severe COPD exacerbations, excluding those moderate exacerbations treated only with antibiotics, will be used as a supportive endpoint for the primary endpoint. This supportive endpoint includes all severe COPD exacerbations and moderate COPD exacerbations treated by OCS with or without antibiotics.

9.4.2.2 Proportion of Subjects with ≥ 1 COPD Exacerbation

The proportion of subjects with ≥ 1 COPD exacerbation will be a secondary efficacy variable.

9.4.2.3 Time to First Exacerbation

Time from randomization to the first COPD exacerbation will be a secondary efficacy variable, and is calculated as follows:

Start Date of first COPD exacerbation – Date of randomization + 1.

The time to first COPD exacerbation for subjects who do not experience a COPD exacerbation will be censored at the time point after which an exacerbation could not be assessed. For subjects lost to follow-up or prematurely withdrawing from the study, the time to first COPD exacerbation will be censored at the end of the maximum follow-up time, as described in Section 9.4.2.1.

9.4.2.4 Annual Rate of Severe COPD Exacerbations

The annual rate of severe COPD exacerbations will be a secondary efficacy variable. If the cause of any death is related to COPD or a COPD exacerbation, the event will also be included.

In the statistical analysis, the number of severe COPD exacerbations will be used as response variable, and the logarithm of the subject's corresponding follow-up time will be used as an offset in the analysis to adjust for subjects having different observation times during which the events occur.

Follow-up time is derived as described in Section 9.4.2.1.

Time to first severe COPD exacerbation and proportion of subjects with at least one severe COPD exacerbation will be used as supportive variables to this secondary efficacy variable.

9.4.2.5 Forced Expiratory Volume in 1 Second

The change in FEV₁ from baseline to each of the post-randomization visits up to and including the Week 52 visit (Visit 16) will be assessed with change from baseline at week 52 used as the secondary efficacy variable. The last pre-bronchodilator measurement recorded prior to the first dose of IP will be used as baseline FEV₁.

9.4.3 Calculation or Derivation of Safety Variables

9.4.3.1 Safety Variables

The following safety data will be collected: vital signs, physical examination, 12-lead ECG, hematology, clinical chemistry, urinalysis, and reported AEs.

Change from baseline (last measurement prior to first IP administration) to each post-treatment time point where scheduled assessments were made will be calculated for relevant measurements. AEs will be summarized by means of descriptive statistics and qualitative summaries.

9.4.3.2 Adverse Events

Adverse events experienced by the subjects will be collected throughout the entire study and will be coded by the AstraZeneca designee using the latest version of the Medical Dictionary for Regulatory Activities (MedDRA).

Adverse event data will be categorized according to their onset date into the following study periods:

- AEs occurring during screening (onset date ≥ Visit 1 and before the first dose of study treatment)
- AEs occurring during treatment (onset date \geq the first day of study treatment and \leq the last day of study treatment + 4 weeks)
- AEs occurring during follow-up
 - (onset date > the last day of study treatment + 4 weeks and ≤ the last day of study treatment + 16 weeks)

The timing of AEs will be assigned to the period in which they first occurred. If an AE has a missing onset date, then unless the stop date of the AE indicates otherwise, this will be considered an on-treatment event. Similarly, if an AE has a partial onset date, then unless the partial onset date or the stop date indicates otherwise, this will be considered an on-treatment AE.

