8.3.4 Adverse Event Data Collection

The following variables will be collected for each AE;

- AE (verbatim)
- The date when the AE started and stopped
- Whether the AE is serious or not
- Investigator causality rating against the IP(s) (yes or no)
- Action taken with regard to IP(s)
- Select the appropriate as required: AE caused subject's withdrawal from study (yes or no)
- Outcome

In addition, the following variables will be collected for SAEs:

- Date AE met criteria for serious AE
- Date Investigator became aware of serious AE
- Reason of AE being considered serious
- Date of hospitalisation
- Date of discharge
- Probable cause of death

- Date of death
- Autopsy performed
- Causality assessment in relation to study procedure(s)
- Causality assessment to other medication(s)

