Appendix B Adverse Event Definitions and Additional Safety Information

B 1 Definition of Adverse Events

An adverse event is the development of any untoward medical occurrence in a subject or clinical study subject administered a medicinal product and which does not necessarily have a causal relationship with this treatment. An AE can therefore be any unfavourable and unintended sign (e.g., an abnormal laboratory finding), symptom (for example nausea, chest pain), or disease temporally associated with the use of a medicinal product, whether or not considered related to the medicinal product.

The term AE is used to include both serious and non-serious AEs and can include a deterioration of a pre-existing medical occurrence. An AE may occur at any time, including screening or washout periods, even if no Study treatment has been administered.

B 2 Definitions of Serious Adverse Event

A serious adverse event is an AE occurring during any study phase (i.e., screening, treatment, follow-up), that fulfils one or more of the following criteria:

- Results in death
- Is immediately life-threatening
- Requires in-subject hospitalisation or prolongation of existing hospitalisation
- Results in persistent or significant disability or incapacity
- Is a congenital anomaly or birth defect
- Is an important medical event that may jeopardise the subject or may require medical treatment to prevent one of the outcomes listed above

B 3 Life Threatening

'Life-threatening' means that the subject was at immediate risk of death from the AE as it occurred, or it is suspected that use or continued use of the product would result in the subject's death. 'Life-threatening' does not mean that had an AE occurred in a more severe form it might have caused death (e.g., hepatitis that resolved without hepatic failure).

B 4 Hospitalisation

Outpatient treatment in an emergency room is not in itself a serious AE, although the reasons for it may be (e.g., bronchospasm, laryngeal oedema). Hospital admissions and/or surgical operations planned before or during a study are not considered AEs if the illness or disease

existed before the subject was enrolled in the study, provided that it did not deteriorate in an unexpected way during the study.

B 5 Important Medical Event or Medical Treatment

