2.1.5 Definition of on-treatment

Efficacy analyses

The main efficacy analyses will use all available data for a subject who qualifies for the FAS, including off-treatment data up to Week 52 for subjects who discontinue IP early.

Some efficacy analyses will also be performed on subjects in the FAS which is restricted to on-treatment data. For this purpose, any efficacy assessment date which occurs between the date of randomisation and minimum (date of last dose of IP + 33 days, date of death, date of study withdrawal) will be considered on-treatment. In particular, this allows a subject who completes treatment according to the protocol to have their Week 52 data included as on treatment, provided Week 52 is within the protocol visit window after the last dose of IP at Week 48.

Safety analyses

Safety analyses will be presented for subjects in the safety analysis set, which is described further in Section 2.1.2.

For this purpose, any adverse event start date, or any safety assessment date (e.g. laboratory, vital signs), which occurs between the date of first dose of IP and minimum (date of last dose of IP + 33 days, date of death, date of study withdrawal) will be considered on-treatment. In particular, this allows inclusion of any safety-related information which may be reported at or generated from the IPD visit to be considered as on-treatment, provided the IPD visit is within the protocol visit window after premature discontinuation of IP.

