3.3.2 Adverse events (AEs) - general

AEs experienced by any subject at any time during the entire study will be coded using the latest version of the Medical Dictionary for Regulatory Activities (MedDRA).

AEs will be separated according to their onset date into the following study periods:

- AEs occurring during screening/run-in period: date of Visit 1 \leq AE onset date $<$ date of first dose of IP
- AEs occurring during on-treatment period: date of first dose of IP \leq AE onset date \leq minimum (date of last dose of IP + 33 days, date of death, date of study withdrawal)
- AEs occurring during post-treatment period (for subjects still being followed up then): date of last dose of IP + 33 days $<$ AE onset date \leq study completion or withdrawal date
- AEs occurring during on-study period: date of first dose of IP \leq AE onset date \leq study completion or withdrawal date

AEs occurring during screening run-in period will be listed only.

If the AE has a completely missing (and unresolvable) onset date, then the AE will be assumed to be treatment-emergent, unless the end date indicates unambiguously that the AE resolved before treatment started. If the AE has a partially missing (and unresolvable) onset date, then the AE will also be assumed to be treatment-emergent, unless either the end date indicates unambiguously that the AE resolved before treatment started, or the partial onset date is in the month/year prior to start of treatment.

For exposure-adjusted summaries of specific AEs, the time at risk for each subject will be derived as the time during the relevant period for analysis during which the subject had no occurrence of that AE. Specifically, for on-treatment AEs, time at risk is defined as:

Time at risk (days) = minimum (date of last dose of IP + 33 days; date of death; date of study withdrawal; date of first adverse event occurrence) – date of first dose of IP + 1

The total time at risk (years) for a treatment group will be derived as the sum of the individual subject's times at risk (days) up to the first adverse event occurrence for that treatment group and divided by 365.25.

In all exposure-adjusted summaries of AEs, multiple occurrences of the same event for a particular subject will not be counted as separate events. A subject will either be considered to have no events of the type being summarised, or one or more occurrences of that event.

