4.2.7.1 Adverse events

AEs will be summarised separately for the on-treatment and on-study periods, as defined in Section 3.1.4 unless stated otherwise. All AE summaries will be presented by treatment group. AEs occurring

during the screening/run-in period, or occurring post-treatment will be listed, but not summarised separately.

An overall summary table will be produced showing the number and percentage of subjects with at least one AE in each of the following categories: any AEs, SAEs, AEs with a fatal outcome, and AEs leading to discontinuation of IP (DAEs). The total number of AEs in the different AE categories will also be presented as well as the number of subjects (i.e. accounting for multiple occurrences of the same event in a subject).

All AEs will be summarised by SOC and PT assigned to the event using the MedDRA dictionary. For each PT, the number and percentage of subjects reporting at least one occurrence of the event will be presented (i.e. subjects with multiple occurrences of the same PT will only be counted once).

Similar summaries by SOC and PT will also be presented for:

- SAEs
- AEs with a fatal outcome
- DAEs
- DAEs casually related to IP
- SAEs leading to discontinuation of IP
- Each AESI category separately
- The most common AEs (defined as those occurring in >3% of subjects in either treatment group) by PT only

All AEs (by PT) will be summarised additionally by causality and maximum intensity. If a subject reports multiple occurrences within each PT, the maximum intensity will be taken as the highest recorded (the order being mild, moderate, and severe) respectively.

Separate listings of subjects with AEs, SAEs, AEs with a fatal outcome, DAEs, SAEs leading to discontinuation of IP, and severe infections will be presented.

Exposure-adjusted AE summaries will be presented by SOC and PT for each of the following (on-treatment summaries only):

- All AEs
- SAEs

- Each AESI separately

In these summaries, the exposure-adjusted rate will be defined for each treatment as the number of subjects in that treatment group reporting the AE divided by the total time at risk for all subjects in that treatment group, the latter as defined in Section 3.3.2. Rates will be reported as events per 100 subject-years.

Events confirmed by the independent adjudication committee (major adverse cardiac events (MACE) and malignancies) will be summarised by treatment group.

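### AEs are placed by onset date only, so an AE kept as one record with run-in onset that turns serious, turns fatal or ends IP after first dose is missing from the by-arm SAE, fatal-AE, DAE and seriousness-defined AESI tables

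*Protocol*

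**What the plan says.** Protocol 9.4.3.2 sorts AEs into screening, treatment and follow-up by onset date and adds: "The timing of AEs will be assigned to the period in which they first occurred". SAP 3.3.2 follows it: "AEs will be separated according to their onset date into the following study periods". On AEs that begin before dosing, the same SAP section says: "AEs occurring during screening run-in period will be listed only". SAP 4.2.7.1 repeats that AEs "during the screening/run-in period, or occurring post-treatment will be listed, but not summarised separately".

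The tables rest on two periods: "AEs will be summarised separately for the on-treatment and on-study periods, as defined in Section 3.1.4 unless stated otherwise". SAP 2.1.5 treats as on-treatment an AE start date "which occurs between the date of first dose of IP and minimum (date of last dose of IP + 33 days, date of death, date of"; the third limit, cut off here, is withdrawal from the study. For safety, the on-study period in SAP 3.1.4 also begins at first dose.

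Two protocol passages bear on how a worsening is recorded. For SAEs, Section 8.3.4 collects "Date AE met criteria for serious AE" as a field separate from the AE start date. Appendix B 1 says that an AE "can include a deterioration of a pre-existing medical occurrence".

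**The concern.** AEs are collected from consent (protocol 8.3.2), and the run-in lasts 35 days, or 31 to 49 with the general adjustments. Some subjects with a non-pneumonia respiratory infection in that time may stay in screening and go on to be dosed (protocol 5.4). An AE can therefore be open at first dose and worsen on drug. Neither document has a clause for AEs that worsen after dosing. SAP 3.3.2 uses the term treatment-emergent only to deal with missing or partial onset dates.

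At stake are the tables that readers use to judge serious harm. Serious infections and serious cardiac events are named important potential risks in protocol Table 3, and SAP 8.1.4 and 8.1.6 define both by whether serious criteria were met. The DAE table has a particular difficulty: IP can be stopped only after it has been started, yet a DAE with run-in onset is not counted. The DAE and fatal-AE tables can then disagree with the disposition table, which shows discontinuations and withdrawals by arm and reason without an onset filter.

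**Working it through.** The plan states no figure on this point, so there is nothing to reproduce. The check applies the written period rules to test cases.

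**Rules (SAP 2.1.5, 3.1.4, 3.3.2), with day 1 = first dose**
- Screening, listed only: onset before day 1.
- On-treatment: onset from day 1 to the earliest of last dose + 33 days, death or withdrawal.
- On-study: onset from day 1 to study completion or withdrawal.

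**Cases.** For a completer, last dose is day 337, so on-treatment runs to 337 + 33 = day 370, and the study ends on day 449. In the fatal case, last dose is day 57 and death is day 60, so on-treatment ends at min(57 + 33, 60) = day 60.

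| Case | Placed by onset (as written) | Placed by date the criterion was met |
|---|---|---|
| Onset 10 days before first dose, serious on day 20 | Screening, listed only | On-treatment and on-study |
| Onset 10 days before first dose, fatal on day 60 | Screening, listed only | On-treatment and on-study |
| Onset day 1, serious on day 20 | On-treatment and on-study | On-treatment and on-study |
| Run-in AE whose worsening is opened as a new AE on day 20 | On-treatment and on-study | On-treatment and on-study |

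Only the first two rows change. They need a known pre-dose onset and a worsening kept in the same record.

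**Tables that inherit the gap**
- In SAP 4.2.7.1, the SAE, fatal-AE, DAE and AESI summaries are subsets of the period-restricted AEs.
- The exposure-adjusted tables there, and the pandemic-phase tables in SAP 8.4, use the on-treatment period only.
- SAP 8.1.1 explicitly requires onset within the analysis period for serious hypersensitivity. SAP 8.1.4 and 8.1.6 do not say when serious criteria must have been met, so the general onset rule applies.

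**Time at risk.** SAP 3.3.2 ends time at risk at the first occurrence of the event. With onset 10 days before first dose, the formula gives −10 + 1 = −9 days. With the day-20 serious date it gives 19 + 1 = 20 days. Any added event therefore needs the later date for its time at risk as well.

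**Scale, on assumption only.** The documents give no AE rate and no rate of worsening. If 0.5% to 3% of subjects had such an event (assumed), an arm of 169 would have 169 × 0.005 = 0.8 to 169 × 0.03 = 5.1 of them. The chance of at least one in an arm, 1 − (1 − p)^169, would be 57% to 99%.

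**The case against.** The strongest reply is that the gap depends on how sites record a worsening. No passage says that an AE which later turns serious stays one record. The separate serious-criteria date shows that one record can change status, but that field is needed anyway for AEs that begin on drug. Other text points towards a new record: the AE definition in Appendix B 1 covers deterioration, and protocol 8.3.7 has new or aggravated examination findings reported as AEs. A new record has a post-dose onset and is counted. This stands as a limit on the point, but it does not remove it, because no passage requires a new record.

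The events also remain visible. SAEs, fatal AEs and DAEs are listed. Reasons for stopping IP and for leaving the study are tabulated by arm. Adjudicated MACE and malignancies have their own by-arm summary. The anaphylaxis part of the hypersensitivity AESI is timed against the injection, so a run-in onset hardly arises there. All of this is correct. However, protocol 8.4.7 also sends serious cardiac events and deaths to adjudication, and SAP 4.2.7.1 names only MACE and malignancies for the adjudicated summary.

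A reader might take the run-in's share of study time as the share of serious events lost. The documents do not support that. It assumes uniform onset, an AE rate and a rate of worsening, none of which is given. It also ignores selection before dosing: pneumonia and suspected or confirmed COVID-19 cause screen failure, unstable cardiac and other disorders are excluded, and IP is withheld for fever or an intercurrent illness judged unsafe.

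Finally, reassigning every SAE, fatal AE and DAE to the date of the criterion would do harm. An AE with onset on drug that turned serious or fatal more than 33 days after last dose would leave the on-treatment tables, including the exposure-adjusted ones. That objection stands, and it is why the repair must only add events.

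**Conclusion.** The point holds in a conditional form. Under the written rule, a single AE record with a known pre-dose onset that first meets serious criteria, becomes fatal or leads to IP discontinuation after first dose is listed but not counted in the corresponding by-arm tables. A completely missing onset date is normally treated as treatment-emergent (SAP 3.3.2), so the gap concerns known pre-dose onsets.

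The consequence is under-counting. The rule is identical in both arms, so a reader should not infer a built-in bias between arms, nor that the data are lost. The size cannot be computed from the documents; the 0.8 to 5.1 subjects per arm above only illustrates an assumed incidence. The case for acting is that serious events may be few in arms of this size, that counting now depends on site habit, and that the repair is cheap.

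**What to change.** Amend SAP 3.3.2, 4.2.7.1 and 8.1, and protocol 9.4.3.2 to match. If only the SAP is amended, record the change in SAP Section 6, which now states that there are none.

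- Keep onset date as the rule for all AEs.
- Add that an AE with pre-dose onset which first meets serious criteria, has a fatal outcome or leads to IP discontinuation on or after first dose is also counted in the matching SAE, fatal-AE, DAE and serious infection, cardiac or hypersensitivity AESI tables.
- Place it by the date it met serious criteria or the date of death. Place a DAE in the on-treatment period. No separate stop date is then needed, which matters because protocol 8.3.4 records the action taken with IP but lists no date for it.
- Use the same date for time at risk in the exposure-adjusted SAE and AESI tables. DAEs have no exposure-adjusted table of their own in SAP 4.2.7.1.
- Footnote these events.
- Do not move any AE with on-treatment onset to a later period.

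The cost is wording and a small programming change using data already collected. The downside is that a few events which began before dosing enter these tables. Such a subject may also appear in the SAE row without appearing in the any-AE row, which the footnote should explain.
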